### 6.3 Power analysis for subgroup analysis

For testing the main effect of subgroup levels (eg, OAT vs. CHC) on the SVR outcome with the planned N=600 mITT sample size, the minimally detectable effect size will be approximately 9%-point difference between the subgroup levels which is the same as the power analysis addressed in section 4.5.

For testing significance of DOT vs. PN in each subgroup (e.g., OAT or CHC), however, the minimally detectable effect size of DOT vs. PN will depend on the sample size of each subgroup. For instance, if we assume that a subgroup (e.g., OAT) has 50% of the total mITT sample (i.e., N=300) and that a base SVR rate is 80%, then  $\geq 12\%$  difference will be detected in a multivariable logistic regression model in which adjusting variables explain 10% of variation in the predictor variable. This power analysis also applies to detect binary factors associated with outcome from within-arm subgroups analyses (e.g., OAT vs. CH in DOT or PN arm) since the mITT sample size of each arm will be N=300. For subgroups with smaller sample sizes, the minimally detectable effects sizes will be larger. For example, some of our subgroups will be as small as 20% (N= 120) of the sample (e.g., HIV/HCV coinfected), minimum effect sizes of SVR are larger at  $\geq 157\%$ .

## 7 Exploratory Mediated DOT or PN effects

Mediator analysis will be conducted to identify potential mediators between the DOT/PN effect and each of the SVR. A mediator will be a variable whose value changes or occurs between the baseline and the end of the study; for example, reduced shame, changes in social support, and increased self-efficacy. The potential mediating effects will be assessed by differences in DOT or PN effect sizes depending on outcome between with and without a potential mediator variable in statistical models. Their significance will be tested following the Baron and Kenny mediation test principle. The choice of specific potential mediators will be determined based on discussion with HERO investigators.

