#### **8.6.2 Visit 6: week 36, ± 14 days**

Research staff will assess for factors of interest by administering the following questionnaires:

- Behavioral risk assessment (assesses injection behaviors)
- Shame scale (assesses shame)

Collect the following samples:

- Collect 20 mL of whole blood in EDTA tubes to send to Quest Diagnostics for HCV viremia testing and for archiving.

Provide the following services:

- Counseling on avoidance of HCV transmission and HIV infection.
- Information on drug treatment and needle exchange programs, and other referrals as needed

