## 11.9 Mediated mDOT or PN effects

Mediator analysis will be conducted to identify potential mediators between mDOT/PN effect and each of the five outcomes. A mediator will be a variable whose value changes or occurs between the baseline and the end of the study; for example, reduced stigma and shame, extent of peer support, changes in social support, and increased self-efficacy. The potential mediating effects will be assessed by differences in mDOT or PN effect sizes depending on outcome between with and without a potential mediator variable in statistical models. Their significance will be tested following the Baron and Kenny mediation test principle.

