### 5.2 SVR determination process

SVR will be determined for each participant in the ITT sample, and thus for the mITT and PP samples as well. First, the time window for relevant viral load data for determination of SVR is set at between post-EOT (end of treatment) 10 week (or 70 days) and post-EOT 1 year (or 365 days). This time frame is further divided into two windows: the primary time window (post-EOT 70 days to 98 days) and the secondary time window (post-EOT 99 days to 365 days) (Figure 1). SVR status will be declared based on viremia data collected from the medical chart reviews or bio-repository data and classified into the following three categories: Success, Failure, and Undetermined. Detailed algorithm for the SVR determination process within the primary and secondary time windows is described in Figure 2.

Figure 1. Hero Study Post-EOT Timeline for SVR Determination

[figure not shown]
[figure not shown]

Figure 2. SVR Determination Process

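### SAP 7 lets a mediator of SVR be measured after SVR: shame, its first example, is not repeated until week 36. Separately, stigma (Protocol 11.9) is measured only at baseline.

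*SAP*

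**What the plan says.** SAP 7 defines the candidates by a time span only, and puts shame first among its examples: "A mediator will be a variable whose value changes or occurs between the baseline and the end of the study; for example, reduced shame". The full list of examples is: "for example, reduced shame, changes in social support, and increased self-efficacy". The outcome is SVR, and significance is to be judged by the Baron and Kenny approach, comparing the arm effect with and without the mediator in the model. The section is labelled exploratory and leaves the list open: "The choice of specific potential mediators will be determined based on discussion with HERO investigators". It does not say which visit supplies the mediator value.

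Protocol 11.9 has the same definition, applied to five outcomes, with a longer list of examples: "reduced stigma and shame, extent of peer support, changes in social support, and increased self-efficacy".

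SAP 5.2 fixes when SVR is read, counting from the end of treatment (EOT): "the primary time window (post-EOT 70 days to 98 days) and the secondary time window (post-EOT 99 days to 365 days".

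On the visit side, Protocol 8.6.2 lists "Shame scale (assesses shame" at week 36. That is its first appearance after baseline.

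**The concern.** A mediator has to take its value before the outcome it is meant to explain. The definition in SAP 7 does not require this. It accepts any change up to the end of the study, long after SVR12 is known.

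The later visits describe the shame instrument as concerning shame linked to HCV infection (Protocol 8.6.9 and 8.6.13). Being told of cure could plausibly lower that score. If a score taken after SVR is added to the SVR model, the arm coefficient may shrink because the score reflects cure, and the comparison of models would read this as mediation. At stake is an exploratory statement about how DOT or PN works, not whether one does better than the other.

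Stigma is a different problem. If the scale is given once, a reduction cannot be calculated.

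**Working it through.** The documents give no power or sample-size figure for the mediation analysis, so there is none to reproduce. The check compares visit timing with SVR timing.

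**Inputs**
- Planned course: 84 days (SAP 8.3), so EOT is taken as day 84 from treatment start.
- SVR windows: 70 to 98 days and 99 to 365 days after EOT (SAP 5.2).
- Follow-up visits are counted from treatment start (Protocol 8.6).
- Visit 4: week 12 ± 7 days (8.5.1.c). Visit 5: week 24 ± 14 days (8.6.1). Visit 6: week 36 ± 14 days (8.6.2).

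**SVR windows in days from treatment start** (EOT + offset)
- Primary: 84 + 70 = 154 to 84 + 98 = 182, which is weeks 22 to 26. Visit 5 is 168 ± 14 = 154 to 182, the same span.
- Secondary: 84 + 99 = 183 to 84 + 365 = 449, up to about week 64.

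**When each named construct is measured** (Protocol 8.2, 8.5.1 and 8.6)

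| Construct | Named in | Baseline | Later measurements |
|---|---|---|---|
| Shame | SAP 7, Protocol 11.9 | yes | weeks 36, 120, 168 |
| Stigma | Protocol 11.9 only | yes | none |
| Social support | both | yes | weeks 12, 48, 120, 168 |
| Self-efficacy (health efficacy scale) | both | yes | week 12 |
| Peer support | Protocol 11.9 only | no scale listed | attendance kept in a site log (Protocol 6.3) |

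**Shame against SVR**
- First repeat: 36 × 7 = 252, ± 14 = days 238 to 266 from treatment start.
- Gap after the primary window closes: 238 − 182 = 56 days at least.
- For the earliest repeat to fall inside the primary window, EOT + 98 must be at least 238. EOT would then be day 140 (week 20) or later, against a planned 12 weeks. Stopping treatment early moves the SVR window earlier and widens the gap.

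**Secondary window.** It spans days 183 to 449, so it contains Visit 6. A participant whose SVR is settled by a viral load at week 48 (days 322 to 350) or week 60 (days 406 to 434) would have shame recorded before the deciding sample. A participant settled at week 24 would have it recorded after. Even in the first case, shame is recorded 238 − 84 = 154 to 266 − 84 = 182 days after treatment ended, which is 22 to 26 weeks.

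**Candidates that pass.** Visit 4 is 84 ± 7 = days 77 to 91. The gap to the opening of the primary window is 154 − 91 = 63 days at least, so the week-12 values of social support and health efficacy precede SVR. For someone who stops early, the window opens at EOT + 70, and a Visit 4 as late as day 91 precedes it only if EOT is after day 91 − 70 = 21.

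**Check against Table 3.** The columns are displaced in the extracted copy. A literal count puts the first shame repeat at week 24, but the same block puts health efficacy and the working-alliance form at week 8, whereas the visit text has both at week 12. A one-column shift explains all three. Even week 24 would coincide with SVR12 and not precede it.

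**The case against.** The strongest reply is that SAP 7 is exploratory, that shame is only an example, and that the investigators will choose the mediators later. Protocol 11.12.3 already limits the information-motivation-behavioural (IMB) mediators to change from baseline to the intervention period, so the team knows the principle. All of this is true, and it limits the weight of the point. It does not remove it: that limit is set for IMB mediators, with adherence as the example, and is not carried into SAP 7. With an open list, the definition is the only safeguard on what gets chosen.

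Several stronger readings are tempting and are not supported:

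- *Shame cannot be causal, or the direction is reversed.* Late measurement means mediation is not identified; it does not show that cure changed shame. In the secondary window, the week-36 score may precede the deciding viral load.
- *Stigma is another example of a mediator measured too late.* It is never measured again, so its effect is not estimable. It is also named only in Protocol 11.9, not in SAP 7.
- *Only social support and self-efficacy can be available before SVR.* Protocol 11.9 names five constructs. The fifth, peer support, rests on attendance logs that may well predate SVR.
- *Shame should be deleted throughout.* Protocol 11.9 covers five outcomes. It does not list them, but reinfection is among the trial's secondary outcomes, and a week-36 score can precede a later reinfection.
- *The study ends at week 168 for everyone.* SAP 7 does not define the term, and the visits after week 120 are a separately consented extension (Protocol 8.6.9). Both dates are far beyond week 26, so the conclusion is the same.

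**Conclusion.** The point holds, and it is a fault in a stated rule rather than a missing detail. As written, SAP 7 allows a variable measured after SVR to be tested as its mediator, and its first example is one. The scheduled data cannot identify a change in shame as mediating SVR settled in the primary window, because the first repeat comes at least 56 days after that window closes. Where SVR is settled only in the secondary window, the order of shame and SVR would differ between participants within one model. Reduced stigma, in Protocol 11.9, cannot be computed for any outcome.

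The reach is limited. The analysis is exploratory, and neither the primary SVR comparison nor the other arm comparisons depend on it. A reader might infer that the whole mediation plan fails; it does not, because social support and health efficacy are sound candidates if their week-12 values are used.

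This rests on an 84-day course, on visits made within their windows, on the visit text rather than the displaced Table 3, and on the health efficacy scale being the measure meant by self-efficacy.

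**What to change.** - In SAP 7, define a mediator of SVR as change from baseline to a named visit no later than the end of treatment (Visit 4, week 12), in line with the limit in Protocol 11.12.3.
- Name the week-12 values of social support and health efficacy as the ones to be used. Social support is also scored at weeks 48, 120 and 168, so the visit has to be stated. Say how the analysis treats participants whose treatment ended by day 21, for whom an on-time Visit 4 may not precede the SVR window.
- Remove shame as a mediator of SVR. It may be reported descriptively, or kept for outcomes that occur after it is measured, such as reinfection after week 36.
- Remove reduced stigma from the examples in Protocol 11.9, because no change score exists.

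The cost is a few sentences in the SAP and one phrase in the protocol; the protocol change needs ethics approval before use (Protocol 14.2). No data collection changes. What is lost is shame as a candidate mediator of SVR.

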## 11.4 Sample Size Determination

Sample size N=300 per arm, or a total of N=600, was determined based on feasibility of recruitment from all sites during the study period. Power analysis for each hypothesis below is conservatively conducted based on a reduced sample size (N= 270 per arm, or N=540 in total) after considering 10% attrition rates. The target power is 80% with a two-sided significance level of 0.05. To this end, minimally detectable effect sizes and widths of 95% confidence intervals were computed with those parameters and the sample size after attrition.

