#### 5.4 Statistical Model

Multivariable logistic regression will be applied to test the overall effectiveness of DOT or PN on the SVR (success vs. failure) as the primary outcome. The arm indicator will serve as the primary predictor. The CONSORT and ICH-9 statistical analysis guidelines suggest that, any baseline characteristics, even if significantly unbalanced between arms, should not be included in the multivariable logistic model since baseline imbalance could be due to chance rather than systematic bias in randomized studies but include as the covariates the randomization stratification variables. In the HERO study, they are: site/city, clinic type (OAT and CHC) and stage of liver disease (cirrhosis vs no).

The primary mITT sample, nonetheless, might no longer represent a randomized pool of participants since the characteristics of participants who initiated treatments may be unequal between the two models of care which may have differential effects on triggering treatment initiations due to difference in modalities of treatment initiation and delivery. Therefore, there could exist baseline characteristics that are unbalanced beyond chance among initiated participants between the two arms. We will declare imbalance if a baseline characteristic is significantly different between the two arms with a two-sided p-value < 0.01 considering the multiplicity of testing. As such, we will include unbalanced baseline characteristics for adjusting purposes in multivariable models in addition to the randomization stratification variables, resulting in the following model:

$$\text{Logit}(P(\text{SVR})) = b_0 + b_1 * \text{TRT} + b_2 * \text{Site1} + \dots + b_8 * \text{Site7} + b_9 * \text{Clinic\_Type} + b_{10} * \text{Cirrhosis}$$

+ Unbalanced Covariates

We will consider exploring other methods to adjust potential imbalance using propensity scores or inverse probability weighting.

For the analysis of the secondary ITT sample, we will only include the randomization stratification variables following the CONSORT and ICH-9 statistical analysis guidelines since the ITT samples are purely randomized participants, resulting in the following model:

$$\text{Logit}(P(\text{SVR})) = b_0 + b_1 * \text{TRT} + b_2 * \text{Site1} + \dots + b_8 * \text{Site7} + b_9 * \text{Clinic\_Type} + b_{10} * \text{Cirrhosis}$$

For the analysis of PP model the approach applied to the analysis of the mITT sample will be applied.

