Review of the monthly enrollment reports during the conduct of the study, however, consistently revealed that few participants have cirrhosis to the extent that there are sites and clinics without any randomized participants with cirrhosis. This imbalance raises a concern with respect to the logistic model fitting which may not result in convergence in regression coefficient estimation algorithms due to a potentially ill-conditioned data matrix. If this occurs, we plan to

remove the cirrhosis term in the above model and fit the following model as the primary multivariable model that include only sites and clinic types for adjusting purpose.

$$\text{Logit}(P(\text{SVR})) = b_0 + b_1 * \text{TRT} + b_2 * \text{Site1} + \dots + b_8 * \text{Site7} + b_9 * \text{Clinic\_Type}$$

+ Unbalanced Covariates

We will report the adjusted odds-ratio (OR) with a 95% confidence interval (CI) for the estimate of the DOT vs. PN effect on SVR. We will also compute 95% CIs for the overall and arm-specific SVR rate using an exact (Clopper-Pearson) method to compare with results from other trials. Again, this analysis will be repeated for each of the three analytic samples albeit with different adjusting variables depending on the constituency of the samples: mITT, ITT and PP.

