### 5.5 Power analysis

The HERO study was planned to recruit N=300 participants in each arm in the mITT sample. Considering the base 80% SVR rate in the PN arm, a minimum difference of 9% between the two arms will be detected (i.e., 89% vs. 80%, OR=2.1) with the planned sample size in a multivariable logistic regression model in which adjusting variables explain 10% of variation in the predictor variable. This study posits that a >9% difference in SVR between the PN and DOT groups will be clinically significant based on studies that showed that SVR in treatment naive patients was >90%.

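### Judging mediation of SVR by the arm effect with and without the mediator mixes mediation with non-collapsibility of the odds ratio; it can hide or reverse real mediation when the mediator is strong and the arm shift small

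*SAP*

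**What the plan says.** SAP section 7 sets the aim: "Mediator analysis will be conducted to identify potential mediators between the DOT/PN effect and each of the SVR". The candidates are illustrated, "for example, reduced shame, changes in social support, and increased self-efficacy", and the final choice is left to later discussion among the investigators. The mediating effect is to be "assessed by differences in DOT or PN effect sizes depending on outcome between with and without a potential mediator variable in statistical models". On testing: "Their significance will be tested following the Baron and Kenny mediation test principle". The section title calls the analysis exploratory.

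Protocol 11.9 has the same two rules for each of five outcomes, without the exploratory label.

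Section 7 names no model or effect scale. SAP 5.4 specifies only multivariable logistic regression for SVR, and its reporting rule is: "We will report the adjusted odds-ratio (OR) with a 95% confidence interval (CI) for the estimate of the DOT vs. PN effect on SVR".

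Protocol 11.12.3 adds bootstrap intervals for mediators from the information-motivation-behavioral (IMB) model, with adherence as the example. It too works from changes in the arm coefficient, in mixed effects models.

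**The concern.** The odds ratio is non-collapsible. If a variable predicts SVR and the arm effect is not zero, putting that variable in a logistic model pushes the arm log odds ratio away from zero, even when the arm has no effect on the variable. Mediation pulls the coefficient the other way. The difference between the two fits is therefore mediation minus a shift unrelated to mechanism.

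At stake is the account of why one care model outperforms the other. A factor that does carry part of the effect could be reported as carrying almost none, or as a suppressor. Explaining the outcomes is a stated objective (Protocol 3.3).

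**Working it through.** **Inputs from the documents.** SVR is 80% with PN and 89% with DOT (SAP 5.5: "Considering the base 80% SVR rate in the PN arm, a minimum difference of 9% between the two arms will be detected"). The sample is 270 per arm after attrition (Protocol 11.4).

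**Assumptions, not in the documents.** The mediator is standard normal in the PN arm, with an odds ratio for SVR of 1.25 to 4.48 per SD. The arm shifts it by 0 to 0.5 SD. There is no arm-by-mediator interaction, and the stratification covariates are left out of both fits.

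**The plan's own figures.** SAP section 7 gives no figure for mediation. For the borrowed rates, the odds ratio is (0.89/0.11)/(0.80/0.20) = 8.09/4 = 2.02, against a stated 2.1. With 10% of the arm variable explained by covariates, the minimum detectable difference at 80% power is 8.7 points for 300 per arm and 9.2 points for 270. Both round to the stated 9.

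**Step 1: no mediation.** Without the mediator, the arm coefficient is c = ln(2.0227) = 0.7044. With it, solve for intercepts α0 and α1 such that the average of expit(α + βM) over M ~ N(0,1) equals 0.80 and 0.89, where β is the mediator's log odds ratio per SD. The arm coefficient is then α1 − α0 (by Gauss-Hermite integration).

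| OR per SD | β | α1 − α0 | Rise over 0.7044 |
|---|---|---|---|
| 1.25 | 0.223 | 0.7090 | 0.6% |
| 1.5 | 0.405 | 0.7195 | 2.1% |
| 2.0 | 0.693 | 0.7489 | 6.3% |
| 2.72 | 1.0 | 0.7969 | 13.1% |
| 4.48 | 1.5 | 0.9048 | 28.4% |

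For a binary mediator with 50% prevalence the rise is 1.5% at OR 2, 6.9% at OR 5 and 11.8% at OR 10. On the risk-difference scale, standardised over M, the arm effect stays at 9.0 points with or without M, so the indirect effect is exactly 0.

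**Step 2: real mediation.** Let the arm shift M by a SD and keep the marginal rates at 80% and 89%. Then α0 + c′ + aβ must equal α1, so c′ = (α1 − α0) − aβ, and the difference method's mediated share is (c − c′)/c. The benchmark is the total natural indirect effect: 0.89 minus SVR under DOT with M left at its PN distribution, divided by 0.09.

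- OR/SD 2.72, a = 0.1: c′ = 0.7969 − 0.1 = 0.6969, so the share is 0.0075/0.7044 = 1%. Benchmark: (0.89 − 0.8809)/0.09 = 10%.
- OR/SD 4.48, a = 0.1: c′ = 0.9048 − 0.15 = 0.7548, so the share is −0.0504/0.7044 = −7%. Benchmark: (0.89 − 0.8777)/0.09 = 14%.

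Mediated share in percent, difference method / risk-difference benchmark:

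| OR per SD | a = 0.1 | a = 0.2 | a = 0.3 | a = 0.5 |
|---|---|---|---|---|
| 1.5 | 3.6 / 4.4 | 9.4 / 8.9 | 15.1 / 13.6 | 26.6 / 23.4 |
| 2.0 | 3.5 / 7.4 | 13.4 / 15.1 | 23.2 / 23.2 | 42.9 / 40.5 |
| 2.72 | 1.1 / 10.1 | 15.3 / 20.9 | 29.5 / 32.4 | 57.9 / 57.5 |
| 4.48 | −7.1 / 13.7 | 14.1 / 28.5 | 35.4 / 44.4 | 78.0 / 79.9 |

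The sign reverses when aβ is smaller than the shift in step 1. That means a below 0.0445/0.693 = 0.06 SD at OR/SD 2.0, 0.0925/1.0 = 0.09 SD at 2.72 and 0.2004/1.5 = 0.13 SD at 4.48.

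**Step 3: sampling behaviour with no mediation.** In 2,000 simulated trials of 270 per arm, at OR/SD 2.0, 2.72 and 4.48, the arm coefficient rose on average by 0.048, 0.096 and 0.203. It moved by more than 10% in either direction in 38%, 62% and 85% of trials; part of this is chance imbalance in M. It moved toward zero, the direction that looks like mediation, in 22%, 14% and 7%. A test of arm on mediator was significant in 4% to 5%.

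**The case against.** **The text does not fix the scale.** Section 7 speaks of effect sizes in statistical models, and SAP 6.3 uses effect size for percentage points. That is fair. The logistic coefficient is an inference from SAP 5.4, but it is the only SVR model and reported effect that the SAP gives.

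**Baron and Kenny's procedure already guards against this.** A reader might infer that the plan would produce false claims of mediation. The documents do not support that. The shift is away from zero, and the procedure conventionally includes a test of arm on mediator, which only 4% to 5% of no-mediation trials passed. This objection stands, although the SAP does not write the steps out. The same test would also screen out many of the worst cases. With 270 per arm, a 0.1 SD shift has standard error √(2/270) = 0.086, so z = 1.16 and power is about 21%. At 0.2 SD, z = 2.32 and power is about 64%. For mediators that pass, the test does not correct the size or sign of the share.

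**The striking cases need a very strong mediator.** An OR of 4.48 per SD means PN-arm SVR of about 60% at −1 SD and 97% at +1 SD. Nothing in the documents supports that for shame, social support or self-efficacy. This stands too, and is why the range is shown.

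**The bootstrap covers it.** Protocol 11.12.3 gives adherence only as an example, so it cannot be said to exclude SVR. But a bootstrap of a change in coefficients gives an interval around the shifted quantity and leaves the shift in place.

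**Conclusion.** The concern holds in a conditional form. With a logistic model, the stated rule does not isolate mediation of SVR whenever the arm effect is non-zero and the mediator predicts SVR. If the arm effect is null, there is no systematic shift.

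The size depends on assumptions that the documents cannot settle. The no-mediation shift is 0.6% to 6% of the arm log odds ratio for mediators up to OR/SD 2.0, and 13% to 28% for strong ones. Strong mediators with small arm shifts are where mediation is hidden or reversed.

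A reader might conclude that the method always understates mediation. It does not. Against the total natural indirect effect, the two agree within about 4 points at OR/SD 2.0 or below and at a 0.5 SD shift, and the difference method is sometimes slightly higher. The gap also reflects the change of scale and the choice of decomposition: at OR/SD 4.48 and a 0.1 SD shift, the pure indirect effect is 19.5% rather than 13.7%.

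The primary SVR comparison is untouched, so this is a worthwhile improvement rather than a threat to the trial's main conclusion.

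**What to change.** In SAP section 7 and Protocol 11.9, for binary outcomes, replace the with-and-without comparison by natural direct and indirect effects on the risk-difference scale. Allow an arm-by-mediator interaction, adjust for baseline variables that may confound mediator and outcome (randomisation does not balance these), and give bootstrap 95% confidence intervals. State which decomposition is reported. Keep the arm-to-mediator test as a reported step.

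The cost is SAP and protocol wording and a little more analysis work, using standard SAS and R procedures. It adds no data collection and does not change the sample size. The method needs an explicit assumption of no unmeasured mediator-outcome confounding; the current method needs it too, without saying so.

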### 11.12.3 Quantitative Analysis

The proposed mDOT and PN interventions are guided by Fisher's IMB model [113-115]. The IMB model asserts that information, motivation, and behavioral skills are fundamental determinants of adherence [113]. The IMB model further specifies that personal and situational characteristics, such as poor psychologic health, substance use, unstable housing, or inadequate access to medical care, may moderate these relationships and impact adherence [113]. In extreme cases, strong negative effects on adherence are expected, and interventions aimed at improving information and motivation may not be effective without adjuvant support. Both interventions - mDOT and PN - focus on enhancing information, motivation, and behavioral skills, and provide adjuvant support to lessen negative impacts of moderating factors. While primarily operating on behavioral skills, the mDOT intervention also enhances both information and motivation (through support from nurses and outreach workers). The PN intervention addresses information (through education), motivation (through PN and peer support), and behavioral skills (PN and peer-led skill-building sessions).

*IMB model mediator analysis.* The analysis will examine if mDOT vs. PN adherence, for example, will be mediated by IMB components. Specifically, IMB model mediators of

adherence will be assessed at baseline, and during the intervention, and will use as the observed values of IMB mediators changes in those variables from the baseline to the intervention period. The indirect effects of IMB mediators will be tested by assessing changes in coefficients of the intervention effect (PN or mDOT) with and without IMB component(s) in mixed effects models. Confidence intervals of the mediated effects will be calculated by bootstrapping, and mediation assumed if confidence intervals do not include zero.

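### Testing mediation by the Baron and Kenny principle, read in its classical form, makes a real indirect effect on SVR hard to detect when the overall DOT vs PN difference is well below 9 points or the paths offset

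*SAP*

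**What the plan says.** SAP 7, headed "Exploratory Mediated DOT or PN effects", gives the measure: "The potential mediating effects will be assessed by differences in DOT or PN effect sizes", with and without the candidate mediator in the model. It then gives the test: "Their significance will be tested following the Baron and Kenny mediation test principle". Reduced shame, changed social support and increased self-efficacy are offered as examples; the final list is left to the investigators. Protocol 11.9 has the same measure and test for five outcomes. Neither section lists the steps, says whether a significant total effect is needed, or plans an interval for the indirect effect on SVR.

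Protocol 11.12.3 sets another rule for mediators from the information-motivation-behavioral (IMB) model, with adherence as the example outcome: "Confidence intervals of the mediated effects will be calculated by bootstrapping, and mediation assumed if confidence intervals do not include zero". It states no condition on the total effect. SAP 7 does not carry this rule over.

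On size, SAP 5.5 says: "The HERO study was planned to recruit N=300 participants in each arm in the mITT sample". With 80% SVR assumed under PN, it gives 9 points (89% vs 80%, OR 2.1) as the detectable difference. Protocol 11.4 adds: "The target power is 80% with a two-sided significance level of 0.05", and bases its power on 270 per arm after attrition.

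**The concern.** The question is whether part of the arm effect runs through a mediator, so the relevant null is that the indirect effect is zero. The classical Baron and Kenny sequence tests first whether the total arm effect is zero and stops if that is not rejected. A trial can have a real indirect effect and a small total effect, either because the whole difference is modest or because a direct path pulls the other way.

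The second case is possible here. Protocol 2.2 (Models of Patient Navigation) suggests that navigation with integrated peer support may improve self-efficacy, shame and stigma, and SAP 7 names shame and self-efficacy as candidate mediators. The SVR hypothesis in SAP 5.1 nevertheless favours DOT. A pathway favouring PN under a total effect favouring DOT therefore fits the trial's own expectations.

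At stake is what the trial learns about mechanism. A null result produced by the first step says nothing about the pathway but could be read as evidence against it. Two sections also apply different decision rules to closely related questions, and candidates such as self-efficacy could arguably fall under either.

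**Working it through.** **1. The plan's own figure.** Inputs: PN 80%, DOT 89%, two-sided 0.05 (SAP 5.5, Protocol 11.4); adjusting variables explain 10% of the variation in the arm indicator (SAP 5.5), so effective n = 0.9 × n. With p̄ = 0.845:

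power = Φ{[0.09 − 1.96·√(2·p̄(1−p̄)/n)] / √[(0.80·0.20 + 0.89·0.11)/n]}

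- SAP, 300 per arm, effective n = 270: (0.09 − 0.0610)/0.0309 = 0.94, power 82.6%; 80% power is reached at 8.7 points.
- Protocol, 270 per arm, effective n = 243: (0.09 − 0.0644)/0.0326 = 0.79, power 78.5%; 80% power is reached at 9.2 points (OR about 2.06).

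The 9-point figure reproduces.

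**2. Chance of passing a total-effect step.** Same formula, effective n = 270:

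| True difference (points) | 3 | 5 | 7 | 8 | 9 |
|---|---|---|---|---|---|
| Chance that the total effect is significant | 14% | 33% | 59% | 72% | 83% |

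An observed difference of about 6.0 to 6.6 points is already significant (effective n from 300 down to 243). Nine points is where power is near 80%; it is not a threshold. The step also caps the procedure: with no true total difference it is passed about 5% of the time, however strong the mediator.

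**3. Detection of a true indirect effect.** Simulation, 2,000 trials per setting, 300 per arm, PN SVR 80%. Assumptions that are not in the documents: one continuous mediator with SD 1; an arm shift of 0.3 or 0.4 SD; a mediator coefficient of 0.4 or 0.5 log-odds per SD; the direct path set to give the stated total difference; no covariates and no mediator-outcome confounding. Without the step, detection means that the arm-to-mediator and mediator-to-SVR paths both have p < 0.05. With it, the total effect must also have p < 0.05.

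| True total difference (points) | 0.3 SD, 0.4 log-odds: without / with the step | 0.4 SD, 0.5 log-odds: without / with the step |
|---|---|---|
| 0 | 93% / 4.5% | 99.6% / 4.8% |
| 3 | 92% / 15% | 99% / 14% |
| 5 | 91% / 33% | 99% / 37% |
| 7 | 90% / 57% | 99.6% / 63% |
| 9 | 90% / 79% | 99% / 86% |

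At 270 per arm the ranges, without vs with the step, are 89-99% vs 5% (0 points), 88-98% vs 31-33% (5 points) and 84-98% vs 72-82% (9 points).

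**4. Interval for the indirect effect.** A separate simulation (1,500 runs, 0.3 SD, 0.5 log-odds) used a Monte Carlo 95% interval for the product of the two paths as a stand-in for the bootstrap. Steps vs interval: 5% vs 96% at 0 points, 16% vs 95% at 3, 37% vs 95% at 5, 84% vs 94% at 9. With the indirect path opposite in sign to the arm effect, the steps detect 5%, 16%, 33% and 81%, against 94-95% for the interval. With one path set to zero the interval rejects in 4.5-5.1%. A Sobel test alone, without the total-effect step, loses only about 3 to 7 points against the interval; this holds for these path sizes and would vary with others.

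**5. Which indirect effect.** SAP 7 and Protocol 11.12.3 both measure mediation as the change in the arm coefficient when the mediator is added. In a logistic model the arm coefficient also moves because odds ratios are non-collapsible, even when the arm does not shift the mediator. Carrying the bootstrap over to SVR with that measure would replace one problem with another.

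**The case against.** The strongest objection is that the step is not in the text. Both sections define the mediating effect as a difference in arm effects and then test the significance of those effects, which could mean a direct, Sobel-type test. This stands as a limit on size: the large losses apply only under the classical reading. It does not remove the point, because the classical reading is the usual one, nothing waives the step, and two statisticians working from the same sentence could apply different rules.

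A reader might infer that any mediated effect is missed whenever the difference is below 9 points. The figures do not support this: true differences of 5 to 8 points pass the step in 33-72% of trials.

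A reader might also infer that the arms work by separate routes, so that offsetting is likely. Protocol 11.12.3 describes both arms as acting on information, motivation and behavioral skills, with different emphasis. Offsetting is possible, not established, and the 0-point rows need a direct path that cancels the indirect one exactly.

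Nor do the documents say that a non-significant result will be reported as absence of mediation; that is a risk of interpretation. Finally, asking for a total effect first is a defensible conservative choice when many candidates are screened at 0.05. That is fair, but the step screens on the wrong hypothesis, and multiplicity is better handled openly.

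**Conclusion.** The point holds as a conditional one. If the Baron and Kenny principle is applied in its classical form, mediation of SVR is unlikely to be detected when the overall difference is well below 9 points or when direct and indirect paths offset. At 300 per arm the fall is to about 5% at no net difference, 14-15% at 3 points and 33-37% at 5, from above 90% in each case. At 9 points it is modest (79-86% vs 90-99%). Under a Sobel-type reading the loss is about 3 to 7 points.

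The first-step probabilities rest on the plan's own inputs. The detection rates rest on assumed path sizes in an idealised model. The mismatch between Protocol 11.12.3 and the other two sections needs no assumption. The importance is low: the analysis is exploratory and the primary SVR test does not depend on it.

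**What to change.** In SAP 7 and Protocol 11.9:

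- State that a significant total arm effect is not required.
- Judge mediation by a bootstrap 95% CI of the indirect effect, the kind of rule already in Protocol 11.12.3.
- Define the indirect effect as the product of the arm-to-mediator and mediator-to-outcome coefficients, or as an indirect effect on the risk-difference scale. Do not use the raw change in the logistic coefficient. Say the same in Protocol 11.12.3 for any binary outcome.
- Report the total effect with its CI alongside, label the result exploratory, and give the number of mediators examined.

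The cost is a few sentences in each document and some computing time, with no new data. The downside is that indirect effects may be reported without a significant total effect and across several candidates, so the wording must be cautious. Mediators are not randomised, and confounding between mediator and SVR remains under either rule.
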